### **9.2.3                   Observation Period**

Each patient will be followed up from the date the ICF is signed until lost to follow-up, withdrawal of consent, death, or the end of the data collection period, whichever comes first. Patients will be followed up for 24 months from the index date, irrespective of whether they continue or discontinue the study treatment.

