**Table 1. Schedule of Assessments**

Assessment	Screening visit	W0 (Index date/ Baseline visit)	Follow-up visits (between W0 to W104) as per routine clinical practice	W104 (end of study)
Informed consent	X			
Inclusion/exclusion criteria	X	X		
Demographics (year of birth, gender)		X		
Physical examination/ vital signs a		X		
Body weight a		X	X	X
Concomitant diseases b		X		
Concomitant medications c		X	X	X
Cancer history d		X		
ECOG performance status		X		
MSKCC risk group e		X		
IMDC risk group f		X		
HRQoL using the NCCN-FACT Fksi-19 questionnaire g		X	X	X
Safety assessment	X	X	X	X
Avelumab plus Axitinib therapy h		X	X	X
Second-line treatment (if Avelumab plus Axitinib discontinued)			X	X
Third-line treatment (if second-line treatment discontinued)			X	X
Treatment response i			X	X
Treatment for AE related to Avelumab plus Axitinib therapy j		X	X	X

AE=Adverse event, ECOG=Eastern Cooperative Oncology Group, HRQoL=health-related quality of life, IMDC=International Metastatic RCC Database Consortium, MSKCC=Memorial Sloan-Kettering Cancer Center, NCCN-FACT Fksi-19=National Comprehensive Cancer Network/Functional Assessment of Cancer Therapy-Kidney Symptom Index 19, W=Week

a Results from physical examinations, vital signs, and body weight will be collected upon availability. Physical examination includes an examination of major body systems. Vital signs include blood pressure (systolic and diastolic) and pulse rate.

b Information on concomitant diseases such as autoimmune disease, cardiovascular disease, hypertension, renal failure, and liver disease.

c Information on concomitant medications such as the use of corticosteroids, anticoagulants, and antibiotics.

d Information on cancer history: age at diagnosis, tumor, node, metastasis (TNM) stage, location of metastases, received nephrectomy, other prior cancer therapies and procedures, expression of the programmed death ligand 1 (PD-L1).

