6.1 Primary Analysis

This analysis will be the main analysis and will include disposition, demographic characteristics, medical and disease history, baseline characteristics, medications and procedures along with summary of exposure, primary and secondary endpoints (limited to the first 12 Months of observation and customized titles and footnotes), summary of safety profile. The detailed list of outputs is reported in [Appendices](#) section.

Primary analysis will be performed after the last participant has completed the 12 months of follow-up from the index date with all applicable study data in-house and related queries resolved, and the database is locked for the analysis.

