6.2 Final Analysis

This analysis will include full set of the analyses and will be performed after the last participant has completed the study with all study data in-house, all data queries resolved, and the database is locked.

7 Changes to the Planned Analyses in the Clinical Study Protocol

With reference to ORR and DCR endpoints, evaluated at 24 months, current IAP will refer the endpoints intended as “up to” 24 months.

8 Analysis Sets and subgroups

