14.2 Further Endpoints

Endpoint Derivations

OS Rate at 24 months	OS rate is defined as the percentage of patients who are alive at 24 months after the index date. OS rate will be presented along with 95% CI.
-----------------------------	--

	Percentage of patients alive at the time of outcome assessment (24 months) will be calculated as per the KM approach.
OS	
OS is defined as the time from index date to the date of death due to any cause. OS for participants without death prior to cut-off will be censored at date of last contact. OS in months is calculated as follows:
 $\text{OS (months)} = [\text{date of death or censoring} - \text{index date} + 1] / 30.4375$ 
Note: If death events occurring after cut-off are to be taken into account, the table below may be used for OS. Nevertheless, this will not be the standard process.
 
OS will be estimated by the KM method. The percentage of censored patients will also be reported. Median event time will be reported, along with 25th and 75th percentiles. Percentage of patients experiencing event or being event-free at applicable timepoints will also be reported along with the corresponding two-sided 95% CIs.
 
Analyses of overall survival time

PFS	
PFS time is defined as the time from index date to the date of the first documentation of objective PD or death due to any cause, whichever occurs first. The tumor response will be determined according to Response Evaluation Criteria in Solid Tumours (RECIST) v 1.1 and assessed by the investigator.
 $\text{PFS time (in months)} = (\text{Date of PD or death} - \text{index date} + 1) / 30.4375 \text{ (months)}$

PFS data will be censored on the date of the last adequate tumor assessment for participants who do not have an event (PD or death) or start a subsequent anti-cancer therapy prior to an event. Participants who do not have any post-baseline tumor assessments will be censored on the start date.

The last adequate tumor assessment is defined as the last tumor assessment result that is not “NE” or “NA”.

The censoring and event date options to be considered for the PFS analysis is presented in below table.

PFS will be estimated by the KM method. The percentage of censored patients will also be reported. Median event time will be reported, along with 25th and 75th percentiles. Percentage of patients experiencing event or being event-free at applicable timepoints will also be reported along with the corresponding two-sided 95% CIs.

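### The SAP states no month-24 limit for the final OS curve, so a few deaths recorded after Week 104 could print a false median OS

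*SAP*

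**What the plan says.** **OS rule.** SAP 14.2 measures OS from the index date to death from any cause. For everyone else, "OS for participants without death prior to cut-off will be censored at date of last contact". Reporting is by Kaplan-Meier, and "Median event time will be reported, along with 25th and 75th percentiles". No month-24 limit appears in this entry.

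**Timing.** The final analysis "will be performed after the last participant has completed the study with all study data in-house" (SAP 6.2). The primary analysis does carry a limit: its endpoints are "limited to the first 12 Months of observation" (SAP 6.1), and the OS outputs in the SAP appendix are titled accordingly.

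**Follow-up.** Protocol 9.2.3 first follows each patient "until lost to follow-up, withdrawal of consent, death, or the end of the data collection period, whichever comes first". It then states: "Patients will be followed up for 24 months from the index date, irrespective of whether they continue or discontinue the study treatment". Data collection runs from July 2021 to May 2025 (protocol section 6).

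**Contacts.** The last column of protocol Table 1 is Week 104, labelled as the end of the study. SAP 9.6 builds the date of last contact from visits and assessments, AE dates, study-drug dates and termination pages. It restricts these to dates tied to actual examinations. A date on which the patient was merely known to be alive is not on the list, and neither are dates of later-line therapy.

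**The concern.** A Kaplan-Meier curve is trustworthy only while patients who die and patients who survive are observed over the same period. Here the two can part after Week 104. A death that reaches the database at month 30 is an event at month 30. A survivor with no examination after Week 104 is censored near month 24, even if the site knows the patient was alive at month 30. Past month 24 the risk set can then consist mainly of patients who are in it because they died.

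Duration of OS is a stated secondary objective, summarised by its median and quartiles. If most patients are alive at 24 months, the correct report is that the median was not reached. Under the visible rules, one or two late deaths could replace that with a specific figure of about two and a half years, which would be easy to quote and wrong.

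**Working it through.** The documents give no expected median OS and, in the current text, no 24-month OS assumption, so there is no figure of the plan to reproduce.

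**Inputs from the documents**
- N of about 100 (protocol 9.5).
- Data collection from July 2021 to May 2025, which is 46 months (protocol section 6).
- Recruitment of about 24 months (protocol 9.1.1). I use 22, because 22 + 24 = 46 lets the last patient reach 24 months by May 2025.
- 24-month visit window, Day 676 to 765 (SAP 9.7).
- 1 month = 30.4375 days (SAP 9.5).

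**Assumptions, not in the documents**
- Exponential survival with 24-month OS of 70%, varied from 60% to 80%.
- Uniform accrual.
- The share of post-Week-104 deaths that are recorded.
- The share of survivors with later contact (none, unless stated).

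**Step 1: exposure past Week 104.** The first patient has up to 46 − 24 = 22 months between the end of scheduled follow-up and the end of data collection.

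**Step 2: how many deaths fall there.** λ = −ln(0.70)/24 = 0.01486 per month, so the true median is ln 2/λ = 46.6 months. The mean probability of being alive at the end of data collection is (e^(−24λ) − e^(−46λ))/(22λ) = (0.700 − 0.505)/0.327 = 0.597. Expected deaths between month 24 and the end of data collection are therefore 100 × (0.700 − 0.597) ≈ 10.3. At 5%, 10% or 20% recording, about 0.5, 1 or 2 of these reach the database.

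**Step 3: why one death is enough.** If a recorded late death is the only patient still at risk, the estimate is multiplied by (1 − 1/1) = 0. The curve drops from about 0.70 to 0 and a median is printed at that date.

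**Step 4: simulation at 70%.** Survivors' last contact was set at Week 104 exactly, within 1.5 months of it, or uniformly over Day 676-765. The ranges cover these choices.

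| Late deaths recorded | Studies printing a median | Typical printed value |
|---|---|---|
| 5% | 35-40% | 29-30 months |
| 10% | 58-65% | 29-30 months |
| 20% | 85-87% | 28-29 months |
| All | 100% | 27.6 months |

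For 24-month OS between 60% and 80%, 10% recording prints a median in about 50-70% of studies, at about 28-30 months. The true medians range from 32.6 to 74.6 months.

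**Step 5: when the problem is absent.**
- *No late deaths beyond routine contact:* a median is printed in 0-2% of runs at 65-80% OS and in about 10% at 60%.
- *OS capped at Week 104, with all survivors observed to that point:* about 0% at 65-80% and 3% at 60%.
- *Deaths and survivors both followed to May 2025:* at 60% a median is printed in 94% of runs, and its typical value is 32.4 months against a true 32.6.
- *In between, at 70% with all late deaths recorded:* late contact for 20% of survivors gives 30.9 months (99% of runs); for 50% it gives 35.6 (86%).

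**Step 6: other estimates.** The mean 24-month OS rate moves by about 0.01 at most. The 12-month rate is not touched.

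**The case against.** A reader might infer that protocol 9.2.3 instructs sites to go on recording deaths, and only deaths, until data collection ends. It does not. Its first sentence covers survivors and decedents alike, and its second sets 24 months for all. Applied consistently, either sentence gives symmetric follow-up. Most of the protocol points to 24 months: 9.1.1, 9.2.5, 9.7.4, the end of Table 1, and the AE recording period in 11.4. If sites close every patient at Week 104, the curve simply ends there.

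That part of the objection stands, and it makes the concern conditional. It does not remove it. The two sentences remain side by side, and SAP 14.2 accepts any death before cut-off. Protocol 11.5 asks for serious events to be followed until the outcome is known, without a Week 104 stop, so a late death can enter. The route is narrow and not exclusive to deaths, since AE end dates also extend last contact for survivors. Even if sites did follow survivors to May 2025, SAP 9.6 would not use a bare confirmation that the patient was alive.

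Three further points are fair. SAP 14.2 mentions an OS table that is absent from the available text, and SAP 9.1 leaves raw-data cut-off rules to a separate document, so a cap in either cannot be excluded. The recording shares are assumed. And SAP section 9 plans numbers at risk with the curves, so an attentive reader could see the thin tail, although the printed median would remain.

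A reader might also extend the point to PFS, PFS2 and DoR. These are censored at the last adequate tumour assessment, a different rule, and nothing here shows the same bias for them.

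**Conclusion.** The concern holds in conditional form. The visible SAP has no month-24 administrative censoring for the final OS curve and percentiles, the protocol leaves two ends of follow-up unreconciled, and the last-contact rule cannot credit survivors with time after Week 104 without an examination-type date. If even 5-20% of later deaths are recorded, a false median near 28-30 months becomes likely enough to matter (roughly 35-87% of studies at an assumed 24-month OS of 70%). If follow-up is closed at Week 104 for all, or kept open for all with survival status recorded and used, the bias is absent.

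The damage is confined to the late curve, median and possibly quartiles of one secondary endpoint in a descriptive single-arm study. The size rests on the assumed survival level, exponential shape and recording share. It should be corrected because the remedy is cheap; it does not threaten the primary result.

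**What to change.** 1. **Protocol 9.2.3:** reconcile the two sentences so that one end of follow-up applies to every patient.
2. **SAP 14.2, if that end is 24 months:** state that in the final analysis OS is administratively censored at a common month-24 limit, that later deaths are listed only, and that no percentile beyond the limit is reported. Define the limit in days and align it with Week 104 and the 24-month rate. A survivor seen exactly at Week 104 has OS of (104 × 7 + 1)/30.4375 = 729/30.4375 = 23.95 months, while 24 months is 730.5 days. Unaligned, such a survivor is censored just before the time point at which the rate is read.
3. **If follow-up to the end of data collection is intended instead:** record survival status for all patients at one common cut-off and add that date to the last-contact list in SAP 9.6.

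Cost: one protocol sentence and one or two SAP sentences. Under option 2 the few deaths after month 24 are not used in the OS estimate, and the median will usually be reported as not reached. Option 3 keeps that information but adds a survival-status contact for each patient.

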### **Progression-free survival:**

- PFS
  - Time interval from the index date to the date of disease progression or death from any cause, whichever comes first
- PFS2
  - Time interval from the index date to the date of disease progression on second-line treatment or death from any cause, whichever comes first

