### **9.7.2 Derived and Transformed Data**

Primary and secondary effectiveness outcomes will be derived as per definition reported in [Section 9.1.2](#).

For OS, PFS, PFS2 and DoR, the percentage of patients alive at the time of outcome assessment (12 or 24 months) will be calculated as per the Kaplan-Meier approach.

For PFS, PFS2 and DoR, a patient progressing after stopping current treatment and starting a new therapy will be censored at the latest tumor assessment showing no progression before changing therapy.

For safety, time to onset of AE will be calculated as difference in days between start date of AE and the index date +1, while duration of AE (applicable for resolved AEs only) will be calculated as difference in days between end date of AE and start date of AE +1.

Time to Avelumab plus Axitinib discontinuation will be derived as difference in days between last dose of Avelumab plus Axitinib and the index date +1 and time to second-line therapy after study treatment discontinuation will be calculated as difference in days between start date of second-line treatment and last dose of Avelumab plus Axitinib +1.

As per NCCN-FACT Fksi-19 scoring guidelines (version 2), the total HRQoL score (range 0-76) will be calculated as sum of single items scores multiplied by 19 and divided by the number of items completed. NCCN-FACT Fksi-19 will also cover 4 subscales: DRS-P (items from 1 to 11, range 0-48), DRS-E (item 12, range 0-4), TSE (items from 13 to 15, range 0-12) and FWB (items from 16 to 19, range 0-12). The higher the subscores or the total score, the better the HRQoL. The subscales will be evaluable, if at least 50% of respective items will be answered and will be calculated as sum of items included in the subscale, multiplied by the item included in the subscale, and divided by the item answered in the subscale. The Fksi-19 questionnaire as a whole will be evaluable, if all subscales will be evaluable and at least 80% of all items will be answered. Score of items 11 (C6), 12 (GF5), and from 16 to 19 (GF1, GF3 and GF7) will be reversed before calculating total and subscale scores.

Every effort will be made to capture all available data by:

- Ensuring that primary variables of interest are those that are routinely collected as part of routine clinical practice and are available via medical charts, physician, and/or patient/caregiver reporting, as appropriate

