#### **9.9 Limitations of the Research Methods**

Treatment response evaluated by RECIST (version 1.1) in real-world observational study may not be as accurate and timely as in a randomized controlled trial. However, the treating physicians will be requested to provide their best judgment on treatment response by evaluating results of patients' radiological investigations.

Despite these limitations, real-world observational data reflects routine clinical practice more closely compared to randomized controlled trials in terms of selection of heterogeneous patient populations and medical treatment they receive. Real-world observational data is essential to assess and improve clinical practice worldwide and complement results of randomized controlled trials. The HRQoL data collected in this study will provide a unique insight into the patient experience and self-assessed impact of the treatment in daily life.

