Table 4 Outcome and event dates for PFS

Scenario	Date of event/censoring	Outcome
PD or death before subsequent anti-cancer therapy	Date of PD or death	Event
PD or death after subsequent anti-cancer therapy	Date of last adequate tumor assessment ^a documenting no PD before subsequent anti-cancer therapy is given	Censored
No PD/Death	Date of last adequate tumor assessment ^a documenting no PD before subsequent anti-cancer therapy is given	Censored
Treatment discontinuation due to 'Disease progression' without documented progression	Not applicable	Information is ignored. Outcome is derived based on documented progression only.
Study end for consent withdrawn without PD or death	Date of last adequate tumor assessment ^a documenting no PD before subsequent anti-cancer therapy is given	Censored

	Study end for lost to follow-up without PD or death	Date of last adequate tumor assessment ^a documenting no PD before subsequent anti-cancer therapy is given	Censored
^a If there are no adequate post-baseline assessments prior to the PD or death, then the time without adequate assessment should be measured from the index date; if the criteria were met the censoring will be on the index date.			
PFS2	
PFS2 time is defined as the time from the index date to the date of disease progression on second-line treatment or death from any cause, whichever comes first. The tumor response will be determined according to RECIST v 1.1 and assessed by the investigator.
 
PFS2 time (in months) = (Date of PD or death after second-line treatment start – index date + 1) / 30.4375 (months).
 
PFS2 data will be censored on the date of the last adequate tumor assessment for participants who do not have an event (PD or death) or start a further subsequent anti-cancer therapy prior to an event. Participants who do not have any post-baseline tumor assessments will be censored on the start date.
 
The last adequate tumor assessment is defined as the last tumor assessment result that is not “NE” or “NA”.
 
The censoring and event date options to be considered for the PFS2 analysis are presented in below table.
 
PFS2 will be estimated by the KM method. The percentage of censored patients will also be reported. Median event time will be reported, along with 25th and 75th percentiles. Percentage of patients experiencing event or being event-free at applicable timepoints will also be reported along with the corresponding two-sided 95% CIs.
		

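### SAP Table 4 censors PFS deaths after a new therapy, an undeclared departure from the protocol definition; because undocumented progressions are also ignored, fixed-time PFS rates are biased upward

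*SAP*

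**What the plan says.** Protocol 9.1.2.2 defines PFS as "Time interval from the index date to the date of disease progression or death from any cause, whichever comes first". SAP 14.2 narrows progression to a documented one and, like the protocol, counts death whatever its cause: "PFS time is defined as the time from index date to the date of the first documentation of objective PD or death due to any" … Neither definition makes an exception for patients who have changed therapy.

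The protocol has one rule for a change of therapy, in 9.7.2: "a patient progressing after stopping current treatment and starting a new therapy will be censored at the latest tumor assessment". The assessment meant is the last one without progression before the change. SAP 9.6 repeats the rule. It names patients who progress after the change and does not mention patients who die.

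SAP 14.2, Table 4, has two rows that matter here:
- "PD or death after subsequent anti-cancer therapy": censored at the last adequate assessment without PD before the new therapy. The accompanying text censors on the index date if there is no post-baseline assessment.
- "Treatment discontinuation due to 'Disease progression' without documented progression": for this row the table's outcome column reads "Information is ignored. Outcome is derived based on documented progression only".

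SAP section 7, on changes from the protocol, has a single entry, which turns the 24-month response endpoints into endpoints over the whole period to month 24: "With reference to ORR and DCR endpoints, evaluated at 24 months, current IAP will refer the endpoints intended as" … It says nothing about PFS.

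**The concern.** There are two separate issues.

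The first is a conflict between documents. Table 4 turns a death after a switch from an event into a censored observation. The protocol definition gives no ground for this, and the SAP does not declare it.

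The second is a bias that arises when the two rows act on the same patient. Someone judged to have progressed, without a RECIST PD on file, and moved to second-line therapy leaves the risk set at the last clean scan. Nothing that happens later can bring that patient back as an event. Such patients are censored because they are progressing, so the censoring is informative.

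The setting makes such patients plausible. Response is recorded only when available (Protocol 9.2.4), visits follow local routine, and Protocol 9.9 concedes: "Treatment response evaluated by RECIST (version 1.1) in real-world observational study may not be as accurate and timely as in a randomized controlled trial". With a single arm, there is no comparator in which the bias could cancel.

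**Working it through.** **Trace of one patient.** Suppose the last scan shows SD at month 6, treatment is stopped at month 8 with reason 'Disease progression' and no documented PD, second-line therapy starts at month 9, and the patient dies at month 14.
- Protocol 9.1.2.2, with PD read strictly as RECIST PD: event at month 14 (death).
- If the recorded stop counted as progression: event at month 8.
- SAP Table 4: the stop is ignored and the death falls in the after-therapy row, so the patient is censored at month 6.

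**Size.** The documents give no expected PFS and no share of undocumented progressions, so there is no plan figure to reproduce. The inputs for an illustration are:
- True median PFS of 13.3 months, exponential. The median is the updated overall-population figure for this combination in Protocol section 7.
- Deaths as 10% of first events (assumption).
- A share p of progressions that are undocumented stops (unknown; 10% and 20% shown).
- All such patients switch at once (assumption).

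If a share f of first events is censored at the event time, the apparent hazard is multiplied by (1 − f). Here f = 0.9p, and 12-month PFS = 0.5^[12(1 − f)/13.3].
- p = 0: 0.5^0.902 = 53.5%
- p = 10%: f = 0.09, 0.5^0.821 = 56.6%
- p = 20%: f = 0.18, 0.5^0.740 = 59.9%

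A Kaplan-Meier simulation of 400,000 patients, with these patients censored at their last 3-monthly scan as Table 4 requires, gives 53.4%, 56.4% and 59.4%.

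**The median.** With documented PD dated at its exact time, the simulated median is 13.3, 14.5 and 15.9 months. With documented PD dated at the next 3-monthly scan, it is 15.0 months at p = 0, still 15.0 at 10%, and 18.0 at 20%. The 12-month rates stay at about 53%, 56% and 59%. The rates therefore rise in both versions, while the median may not.

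**Which rule drives the shift.** At p = 20%, counting only the later death as an event (assumed median of 12 months from switch to death) changes the exact-time median from 15.9 to 15.8 months and leaves 12-month PFS at about 59%. Nearly all of the shift comes from the ignored stops.

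**Scale in this study.** With 100 patients, the expected number of first events by 24 months is 100 × (1 − 0.286) = 71, of which about 64 are progressions. So p = 10% means about 6 patients and p = 20% about 13. The sampling error of a 12-month rate is about √(0.535 × 0.465/100) = 5.0 points, a 95% half-width of about 10 points. The illustrative bias is 3 to 6 points.

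**The case against.** **Ignoring undocumented stops follows the plan's own definition.** Protocol 9.1.2.2 defines PD by RECIST 1.1, and the SAP asks for objective documentation. This stands. A reader might infer that this row of Table 4 is an error, but it is not. Counting such stops as events answers a different question and belongs in a sensitivity analysis.

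**Censoring at a new therapy is a familiar convention.** This also stands, and the protocol itself prescribes it for progression after a switch. It does not explain why deaths are included without being declared. Equally, Protocol 9.7.2 is silent on deaths after a switch. It does not say that they count; only the general definition does.

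**The illustration is close to a worst case.** Patients who do not switch remain under follow-up and become events at PD or death. If 60% switch and the others die with a median of 6 months (both assumed), the exact-time medians at 10% and 20% fall from 14.5 and 16.0 to 14.3 and 15.6 months. Protocol 9.9 also asks physicians for their best judgment of response from radiology, which should reduce the number of undocumented cases.

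**Much is already reported.** Stop reasons are tabulated under SAP 10.1, and the output list has a PFS censoring/event table. What is missing is the link between the two.

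**DoR.** A reader might extend the criticism to Table 6. The protocol ends DoR at documented progression and has no death event, so Table 6 agrees with it.

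**Redaction.** Parts of SAP section 14 are blacked out, so a hidden PFS sensitivity analysis cannot be excluded. In the visible output list for the primary analysis, the blacked-out titles stand beside OS, response and DoR outputs, not PFS.

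**Conclusion.** The point holds in two parts. First, the row of Table 4 that censors deaths after subsequent therapy departs from the protocol's PFS definition and goes beyond the rule in Protocol 9.7.2 and SAP 9.6, and SAP section 7 does not declare it. Second, together with the documented-only rule, it leaves patients who progress clinically and switch without any route to a PFS event, which biases fixed-time PFS rates upward.

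The direction for those rates is secure. The size is not: about 3 points at 12 months if 10% of progressions are undocumented and 6 points if 20% are, given a 13.3-month median, 10% of first events as deaths and an immediate switch by all. No fraction can be taken from the documents.

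A reader might conclude that the rules always lengthen median PFS. That is not supported, because with scan-dated progression and few affected patients the median can stay where it is. Nor does the death rule by itself account for much of the shift. PFS is secondary and descriptive, and the primary 12-month OS rate is unaffected. This is a correction that should be made, not a fatal flaw.

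**What to change.** (a) Reconcile the after-therapy row of Table 4 with Protocol 9.1.2.2 and 9.7.2, or declare the censoring of post-switch deaths in SAP section 7. The text should cover deaths both with and without a documented PD after the switch.

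(b) Keep the RECIST-documented PFS. Beside it, add one prespecified sensitivity analysis in which a stop with reason 'Disease progression' is an event at the discontinuation date, and any PD or death counts regardless of new therapy.

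(c) Tabulate how many patients were stopped for progression without documented PD, with their PFS status.

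For DoR, at most add an optional sensitivity analysis counting stops for progression, without making death an event.

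The cost is SAP wording, one further Kaplan-Meier run and one count on fields already collected. SAP version 1.0 (24 November 2021) predates protocol version 4.0 (24 April 2023), and the SAP requires approval only before database lock, so the change fits in a revision before that point. The downside is that clinical progression is less standardised than RECIST, and the companion PFS estimate may be shorter.
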